13.2. Adverse Events

13.2.1. Definition of Adverse Event

The definitions are adopted in accordance with the Directive 2001/20/EC, ICH-E2A and the European Commission Detailed Guidance 2011/C 172/01.

An **Adverse Event** (AE) is defined as any untoward medical occurrence in a clinical trial subject administered a medicinal product and which does not necessarily have a causal relationship with the treatment.

An AE can therefore be any unfavorable and unintended sign (including any clinical significant abnormal laboratory finding), symptom, or disease temporally associated with the use of an investigational medicinal product, whether or not considered related to the investigational medicinal product.

An **Adverse Drug Reaction** (ADR) means all untoward and unintended responses to a medicinal product related to any dose administered. The phrase ‘response to a medicinal product’ means that a causal relationship has at least a reasonable possibility, i.e. the relationship cannot be ruled out and is judged by the Investigator as at least possible (see definition below).

An **Unexpected Adverse Drug Reaction** (UADR)/**Unexpected Adverse Event** (UAE) means an adverse reaction/event, the nature or severity of which is not consistent with the applicable product information, namely in the Investigator Brochure for an unauthorized investigational product or in the SmPC for an authorized product.

The expected/unexpected status should be evaluated and assessed, by the Sponsor, based on the reference safety information available since expectedness in Pharmacovigilance refers strictly to the information listed or mentioned in the applicable reference safety information and not to events that might be anticipated from knowledge of the pharmacological properties of a substance or because it was foreseeable due to the health status (e.g., age, medical history) of the study subjects.

A **Serious Adverse Event** (SAE) or **Serious Adverse Reaction** (SAR) is defined as an AE that results in any of the following:

- Results in death
- Is life-threatening
- Requires hospitalization or prolongs existing inpatient’s hospitalization
- Results in persistent or significant disability or incapacity
- Results in a congenital abnormality or birth defect
- Is an important medical event which requires medical intervention to prevent any of the above outcomes

SUSARs: AEs which meet all of the following criteria:

- Serious.

- Unexpected (i.e., is not consistent with the applicable product information e.g. Investigator's brochure for an unapproved cytisine or SmPC for an authorised product).
- There is at least a reasonable possibility that there is a causal relationship between the event and the medicinal product.

will be classified as suspected unexpected serious adverse reactions (SUSARs).

Important medical events are those which may not be immediately life-threatening, but may jeopardize the subject and may require intervention to prevent one of the other serious outcomes listed above. Examples of such events are intensive treatment in an emergency room or at home for allergic bronchospasm, or blood dyscrasias or convulsions that do not result in hospitalization.

The term “**life-threatening**” in the definition of “serious” refers to an event in which the subject was at risk of death at the time of the event; it does not refer to an event which hypothetically might have caused death if it were more severe. For example, drug-induced hepatitis that resolves without evidence of hepatic failure would not be considered life threatening even though drug-induced hepatitis can be fatal.

Inpatient **hospitalization** or prolongation of existing hospitalization means that hospital inpatient admission and/or prolongation of hospital stay were required for treatment of AE or occurred as a consequence of the event. It does not refer to pre-planned elective hospital admission for treatment of a pre-existing condition that has not significantly worsened, or to diagnostic procedures.

13.2.2. Recording of Adverse Events

All of the following details will be recorded in the subject’s CRF for each AE:

- Full description of AE.
- Date and time of onset.
- Date and time of resolution.
- Severity of event, to be assessed by an Investigator in accordance with the definitions below.
- Relationship to cytisine to be assessed by an Investigator in accordance with the definitions below.
- Action taken (if any).
- Outcome and details of any further follow-up.

Adverse events documented in the CRF without a stop date should be reviewed at the end of each treatment period until final resolution or until it is medically justifiable to stop further follow up (e.g. a chronic condition has been reached.) Documentation of adverse events should be updated as necessary.

13.2.3. Grades of Adverse Event Severity

The following grades will be used by an Investigator to describe the severity of all AEs (including clinically-significant laboratory AEs) as shown in [Table 8](#). Only 1 severity grade will be used for each AE (e.g. mild - moderate is not acceptable).

Table 8: Adverse Event Severity

Severity of AE	Definition
Mild	No interference with activity
Moderate	Some interference with activity requiring no or minimal medical intervention
Severe	Prevents daily activity and requires medical intervention

If an adverse event has multiple aspects, the aspect in the highest intensity will be graded. It is emphasized that the term severe is a measure of intensity; thus a severe AE is not necessarily serious. For example, itching for several days may be rated as severe; however, may not be clinically serious.

13.2.4. Assessment of Causal Relationship

The causal relationship between an adverse event and **cytisine** will be determined and documented by the responsible Investigator, or designee, according to best medical judgment as shown in ([Table 9](#)).

Table 9: Assessment of Causal Relationship

Category	Description
Not Related	The event is definitely not associated with cytisine.
Unlikely	The event was most probably produced by other factors such as the subject's clinical state, therapeutic intervention or concomitant therapy, and does not follow a known response pattern to cytisine
Possible	The event follows a reasonable temporal sequence from the time of cytisine administration, and/or follows a known response pattern to the investigational product, but could have been produced by other factors such as the subject's clinical state, therapeutic intervention or concomitant therapy.
Probable	The event follows a reasonable temporal sequence from the time of cytisine administration, and/or follows a known response pattern to the product, and could not have been produced by other factors such as the subject's clinical state, therapeutic intervention or concomitant therapy.
Definite	The event follows a reasonable temporal sequence from the time of cytisine administration, and/or follows a known response pattern to the product, and could not have been produced by other factors such as the subject's clinical state, therapeutic intervention or concomitant therapy, and either occurs immediately following investigational product administration, or improves on stopping the investigational product.

13.2.5. Reporting of Serious Adverse Events

Any new SAE that occurs during a treatment period should be recorded and reported immediately. All SAEs including those that are ongoing at the end of study treatment will be followed until each event resolves or is assessed as chronic.

In order to satisfy regulatory requirements, any Serious Adverse Event, whether deemed study drug-related or not, must be reported to the Sponsor or designee as soon as possible after the Investigator or coordinator has become aware of its occurrence. SAE form completion and reporting must not be delayed even if all of the information is not available at the time of the initial contact.

SAEs must be reported within 24 h of knowledge of the event by submitting an initial SAE report via email or fax to [REDACTED]:

Email: [REDACTED]

[REDACTED] will notify the Sponsor and Sponsor's Responsible Physician of the SAE via email within 24 h of receipt of the initial SAE report.

Additional information (follow-up) about any SAE unavailable at the initial reporting should be forwarded by the site within 24 hours of the information becoming available.

The following information should be provided to accurately and completely record the event:

- Investigator name and center number
- Subject number
- Subject initials, if permitted
- Subject demographics
- Clinical event
 - description
 - date of onset
 - severity
 - treatment
 - relationship to study drug (causality)
 - action taken regarding study drug
- If the AE resulted in death:
 - cause of death (whether or not the death was related to study drug)
 - autopsy findings (if available)
- Medical history case report form (copy)
- Concomitant medication case report form (copy)
- Any relevant reports (laboratory, discharge, x-ray, etc.)

Subjects who have had an SAE during the treatment period must be followed clinically until all parameters (including laboratory) have either resolved or been assessed as chronic.

SUSARs should be reported to the REC, MHRA and Sponsor in accordance with applicable regulatory requirements for expedited reporting. It is [REDACTED] responsibility to report SUSARs to the REC and MHRA. It is the Sponsor's responsibility to report any SUSAR to the FDA.

13.2.6. Monitoring of Subjects with Adverse Events

In the event of any abnormalities considered to be clinically significant by the investigating physician, subjects will be followed up with appropriate medical management until:

- It has resolved/returned to normal or baseline.
- The event has stabilised at a level acceptable to the Investigator and is not considered to be clinically significant.

13.3. Pregnancy

Serum pregnancy test will be performed for all females regardless of post-menopausal or sterilised status at screening. Pregnancy tests will be performed by [REDACTED]. Serum pregnancy tests will be performed using the Roche Cobas c6000 analyser series comprising of c501 and e601 modules.

13.4. Laboratory

13.4.1. Routine Laboratory Assessments

Routine laboratory safety samples will be analysed by [REDACTED] at screening and again on Day 5 for each subject. Printed laboratory reports will include normal reference ranges. A decision regarding whether the result outside the reference range is of clinical significance or not shall be made by an Investigator and the report will be annotated accordingly. Clinically significant abnormalities at screening or occurring during the study will be recorded on the AE page. The reference ranges for laboratory parameters will also be filed in the Investigator site file.

Haematology: Haemoglobin (HGB), haematocrit (HCT), mean cell volume (MCV), mean cell haemoglobin (MCH), mean cell haemoglobin concentration (MCHC), red blood cells (RBC), white blood cells (WBC), neutrophils (NEUT), lymphocytes (LYMP), monocytes (MONO), eosinophils (EOS), basophils (BASO) and platelets (PLT).

Biochemistry: Total protein (TP), albumin (ALB), total bilirubin (BIL-T), alanine transaminase (ALT), aspartate transaminase (AST), gamma glutamyl transferase (GGT), alkaline phosphatase (ALKP), glucose (GLU), sodium (NA), potassium (K), calcium (CA), bicarbonate (HCO_3), creatinine (CREA) and urea.

At screening, biochemistry samples will be collected into a z-gel collection tube. The volume will allow sufficient serum for virology and pregnancy test screening. At all other visits, biochemistry safety samples will be collected into a 4.5 mL plain Sarstedt Monovette® collection tube. Biochemistry samples will be analysed using the Roche Cobas c6000 analyser series comprising of c501 and e601 modules.

Urinalysis: pH, specific gravity, protein, blood, glucose, leucocytes, ketones, urobilinogen, bilirubin & nitrites. In the event that the 'dipstick' is positive, RBCs, WBCs, epithelial cells,

crystals, bacteria and casts will be examined microscopically. The microscopy will be performed at [REDACTED] or referred to a local specialist hospital laboratory for analysis.

A mid-stream urine sample will be collected into a 20 mL Sterilin tube. Urinalysis will be performed using the Roche Cobas c6500 analyser series comprising of u601 and u701.

13.4.2. Virology

Virology (Hep B, Hep C and HIV) will be performed at screening.

Virology will be analysed by [REDACTED] using the Roche Cobas c6000 analyser series comprising of c501 and e601 modules.

13.4.3. Drugs of Abuse and Alcohol

Urine alcohol and drugs of abuse screen: Cannabinoids, amphetamines, cocaine, benzodiazepines, opiates and cotinine.

A mid-stream urine sample will be collected into a 20 mL Sterilin tube. At time-points when both urinalysis and drugs of abuse / alcohol screening is required, all testing will be performed from a single 20 mL sample.

Drug of abuse and alcohol samples will be analysed by [REDACTED] using the Roche Cobas c6000 analyser series comprising of c501 and e601 modules. Vital signs

13.5. Vital signs

Systolic/diastolic blood pressure and pulse rate and oral temperature.

Measurements will be recorded in the supine position after 5 min supine. Blood pressure, pulse and temperature will be measured by the DINAMAP* Compact Vital Signs Monitor (Model TS) or equivalent. Normal ranges for vital signs are presented in [Appendix 1](#).

13.6. Physical Examination

A physical examination will be performed by an Investigator. The examination will include general appearance, head, ears, eyes, nose, throat, neck, skin, cardiovascular system, respiratory system, gastrointestinal system, central nervous system, lymph nodes and musculoskeletal. An Investigator can examine other body systems if required, at their discretion.

13.7. ECG Measurements

Screening and discharge ECGs will be conducted using a 12-lead ECG. Heart rate, PR interval, QRS width, QT interval, and QT interval corrected using Fridericia's formula (QTcF) will be documented.

12-lead ECG recordings will be made using a MAC 5500 or equivalent. Each ECG trace should be labelled with the study number, subject number, subject initials and date of birth. An Investigator will provide an interpretation of each tracing. Clinically significant abnormalities will be recorded on the AE page. Normal ranges for 12-lead ECG parameters are presented in [Appendix 1](#).

13.8. Concomitant Medication

All prior and concomitant medications taken during the study will be recorded in the subject's CRF.

14. APPROPRIATENESS OF MEASUREMENTS

All measurements performed in the study are standard measurements.

The total volume of blood to be collected from each subject during the study (approximately 112 mL) is considered acceptable.

Table 8: Summary of Blood Volume

Procedure	Visit	No. Samples	Blood Volume per Sample (mL)	No. Treatment Periods	Blood Volume (mL)
Biochemistry	Screening ^a	1	4.5	1	4.5
	Study Day 5	2	4.5		4.5
Haematology	Screening	1	2.7	1	2.7
	Study Day 5	2	2.7		2.7
PK Drug Conc. Measurement	Treatment Period	18	2.7	2	97.2
Total Blood Volume					111.6

^a From the screening biochemistry blood samples, the serum pregnancy test and virology screen will be conducted.

15. STATISTICAL METHODS

15.1. Primary Objectives and Analysis

All data recorded during the course of the study or derived during the programming phase will be presented in individual data listings.

Unless specified otherwise, continuous variables will be summarised with the following descriptive statistics: n (number of observations), arithmetic mean, standard deviation (SD), minimum value, median and maximum values. For PK summaries, the geometric mean and coefficient of variation (%CV) will also be used to summarise the data. Categorical data will be summarised with frequencies and percentages.

Unless specified otherwise, the minimum and maximum statistics will be presented with the same precision as the original data. The mean, median and geometric mean will be presented to one more decimal place than the original data. The SD will be presented to two more decimal places than the original data. Unscheduled measurements will be listed in the individual data listings. With the exception of baseline, unscheduled measurements will be excluded from the descriptive statistical analysis. In case an unscheduled measurement is performed immediately after the scheduled measurement due to an error in the previous measurement, the unscheduled measurement will be included in the analysis and the original erroneous measurement will be excluded.

For subject characteristics and safety analyses, missing data will not be replaced; descriptive statistics and statistical analysis will be performed on the basis of the available data only.

Subjects discontinued will be included in the descriptive statistics if they have received the investigational product and their examinations were performed at the same scheduled time as other subjects. All data recorded on discontinued subjects will be listed.

15.2. Subject Populations for Analyses

15.2.1. Safety Analysis Set

All subjects who received at least one dose of cytisine will constitute the Safety Set.

15.2.2. PK Analysis Set

- Subjects will be allocated to the PK Analysis Set on a per treatment basis. The PK Analysis Set for a treatment will include all subjects who receive the one dose of cytisine, do not violate the protocol in a way that may invalidate or bias the results (major protocol deviation) and have sufficient plasma concentration-time profiles complying with the following criteria:
- Do not have an occurrence of vomiting or diarrhoea which renders the plasma concentration profile unreliable (e.g. if vomiting occurs at or before 2 times median T_{max});
- Do not use a concomitant medication which renders the plasma concentration profile unreliable;
- Do not have a pre-dose plasma concentration that is greater than 5% of the corresponding C_{max} ;
- Have at least one evaluable plasma concentration that is preceded by a lower evaluable concentration and followed by a lower evaluable concentration for the calculation of C_{max} , T_{max} and AUCs (i.e. at least 3 evaluable concentrations in total).

In order to be included in the statistical comparisons, a subject is required to be included in the PK Analysis Set for both treatments.

15.2.3. Urine Excretion Analysis Set

Subjects will be allocated to the Urine Excretion Analysis Set on a per treatment basis. The Urine Excretion Analysis Set for a treatment will include all subjects who receive the one dose of cytisine, do not violate the protocol in a way that may invalidate or bias the results (major protocol deviation) and comply with the following criteria:

- Do not have any missing urine excretion collections (i.e. missing urine in a collection period specified in Section 12.2) which renders analysis of overall excretion unreliable;
- Do not have an occurrence of vomiting or diarrhoea which renders the urine excretion profile unreliable (e.g. if vomiting occurs at or before 2 times median T_{max} derived from plasma data);
- Do not use a concomitant medication which renders the urine excretion profile unreliable.

In order to be included in the statistical comparisons, a subject is required to be included in the Urine Excretion Analysis Set for both treatments.

15.3. Subjects Characteristics

Demographic data will be summarised (age, height, weight, BMI and race) by gender and overall. Separate summaries of demographics, will be provided for both safety and PK/Urine excretion analysis sets if applicable. Subject disposition and analysis sets (safety, PK) will also be listed and summarised by frequency.

The protocol violations will be listed per subject, describing the nature of the violation. Subjects failing to complete the study (as well as the date and reasons for discontinuation) will be displayed. Time may be added if relevant to the nature of the violation.

Medical history will be referred in accordance with the Medical Dictionary for Regulatory Activities (MedDRA), version 20.0 or higher. Medications will be mentioned according to the Anatomical Therapeutic Chemical (ATC) classification system using WHO Drug Dictionary.

15.4. Sample Size Calculation

A total of 12 subjects will be randomized to the study, with approximately 6 subjects per treatment schedule arm.

Subject numbers are based on the following guidance: In study ACH-CYT-01, geometric mean $AUC_{0-\infty}$ values in the fed and fasted states were 168 ng.h/mL and 173 ng.h/mL respectively (yielding a geometric mean ratio of 0.97) with an intra subject CV% of approximately 6%. Geometric mean C_{max} values in the fed and fasted states were 22.3 ng/mL and 29.8 ng/mL respectively (yielding a geometric mean ratio of 0.75) with an intra subject CV% of approximately 23%. Although this study is not a formal comparison of bioequivalence the assumptions used for a typical bioequivalence study have been used in order to estimate an appropriate sample size. Based on the assumption that similar results will be observed for this study, a sample size of 4 subjects would be sufficient to detect a 20% difference in $AUC_{0-\infty}$ between the treatments with a power of 80%, an alpha of 5% and a fed/fasted ratio of 1. Therefore, 12 subjects, which is the minimum number of subjects recommended for this type of trial, should be sufficient to compare the bioavailability with respect to AUC in the fed and fasted states. Given that the C_{max} geometric mean ratio observed in the previous study did not fall within the bioequivalence range, likely due to the slower rate of absorption in the fed state, the sample size has been based on $AUC_{0-\infty}$.

Subjects who withdraw from the study before receiving any study medication will be replaced. Subjects who are withdrawn from the study due to significant drug-related AEs will not be replaced. Replacement of all other subjects withdrawn from the study after receiving study medication will be decided on a -case-by-case basis by the Principle Investigator (or delegate) and Sponsor.

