3. RATIONALE FOR THE STUDY

In the recent bioavailability study evaluating the original marketed formulation for cytisine, no food effect was observed for $AUC_{0-\infty}$ (or AUC_{0-t}) with values considered bioequivalent as the 90% CI for the difference between fed and fasted states fell within the range 80 -125%. Consistent with this, the amounts of cytisine recovered from urine within 24 h were similar between fed and fasted states, despite C_{max} being lower in the fed state. In that study, it was concluded that there was no clinically significant food effect for cytisine and there were no safety concerns following administration of a single dose of 3 mg cytisine under fed or fasted conditions for healthy non-smokers.

A revised formulation has been subsequently developed, eliminating lactose and introducing lower formic acid containing-excipients, to retard the formation of the breakdown substance *N*-formylcytisine. Initial studies indicate that the revised formulation has improved stability at 24 months and that the shelf-life could be extended to 36 months based on the preliminary stability information. This study will evaluate if there is any food effect for cytisine using this new formulation in healthy smokers.

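### Does the conflict over the earlier study's fasted Cmax (22.9 or 29.8 ng/mL) undermine the sample size or the Cmax analysis?

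*Protocol*

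**What the plan says.** Protocol section 15.4 and SAP section 3.5 draw on ACH-CYT-01, the earlier fed/fasted study of the original formulation. For AUC0-∞ the fed and fasted geometric means "were 168 ng.h/mL and 173 ng.h/mL respectively (yielding a geometric mean ratio of 0.97"), "with an intra subject CV% of approximately 6"%. For Cmax they "were 22.3 ng/mL and 29.8 ng/mL respectively (yielding a geometric mean ratio of 0.75"), "with an intra subject CV% of approximately 23"%.

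From the AUC figures the protocol concludes that "a sample size of 4 subjects would be sufficient to detect a 20% difference in" AUC0-∞, "with a power of 80%, an alpha of 5% and a fed/fasted ratio of 1". It then plans 12, described as the recommended minimum for this kind of trial: "A total of 12 subjects will be randomized to the study, with approximately 6 subjects per treatment schedule arm". Cmax is left out of the sizing because its earlier ratio lay outside the bioequivalence range. Both documents say that the study is not a formal bioequivalence comparison, and they claim that 12 is sufficient for AUC only.

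Table 3 in protocol section 2.2 summarises the same study, with Cmax 22.9 ng/mL fasted and 22.3 ng/mL fed. Its AUC0-∞ values, 173 and 168 ng.h/mL, match section 15.4. Section 3 (Rationale) limits its bioequivalence statement to AUC and says that urinary recovery was similar "despite C_{max} being lower in the fed state".

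**The concern.** One cell conflicts between two accounts of one study. The fed Cmax and both AUC0-∞ values agree, and section 15.4 calls them geometric means, so a different summary statistic in Table 3 is an unlikely explanation.

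The two values tell different stories. With 22.9 the earlier study shows almost no food effect on Cmax; with 29.8 it shows a fall of about a quarter. Cmax stands beside AUC0-∞ in the first primary objective, and the stated reason for not sizing on it is true only with 29.8. If 22.9 were right, that reason would fall away. The plan would then have set aside a primary measure that could have been sized, without saying how precisely 12 subjects can estimate it.

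**Working it through.** **Inputs.** Fed Cmax 22.3; fasted Cmax 29.8 (protocol 15.4, SAP 3.5) or 22.9 (Table 3); CV 23% for Cmax and 6% for AUC0-∞; n = 12 in a two-period, two-sequence crossover; bioequivalence range 80–125% (protocol section 3).

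**1. The plan's own figures.**
- AUC0-∞ ratio: 168/173 = 0.971, stated as 0.97.
- Cmax ratio in 15.4: 22.3/29.8 = 0.748, stated as 0.75.
- Cmax ratio from Table 3: 22.3/22.9 = 0.974.
- Required n for AUC0-∞: two one-sided tests at 5% each, limits 0.80–1.25, true ratio 1, CV 6%, n − 2 degrees of freedom. At n = 4 the exact power is 88.8% (85.8% at a true ratio of 0.97), so the stated 4 reproduces. At n = 12 power is effectively 100%.

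Section 15.4 contains no arithmetic error, and no Cmax value enters the calculation of 4 or the choice of 12.

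**2. Precision for Cmax.** The within-subject SD on the log scale is √ln(1 + 0.23²) = 0.2270. The standard error of the log ratio is 0.2270 × √(2/12) = 0.0927. With t(0.95, 10 df) = 1.812, the 90% half-width is 1.812 × 0.0927 = 0.168, and exp(0.168) = 1.183. This depends on the CV and n, not on the earlier fasted mean.

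| Fasted Cmax | Fed/fasted ratio | Expected 90% interval, n = 12 |
|---|---|---|
| 29.8 | 0.748 | 0.63 to 0.89 |
| 22.9 | 0.974 | 0.82 to 1.15 |

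**3. Chance of detecting the effect that 15.4 anticipates.** At a true ratio of 0.748 the noncentrality is |ln 0.748| / 0.0927 = 0.290/0.0927 = 3.13. From the noncentral t with 10 df, the 90% interval excludes 1 with probability about 90%, and a two-sided 5% test has about 80% power. A Cmax fall of the size reported in 15.4 would usually be seen.

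**4. Power for a bioequivalence-type conclusion on Cmax.** At n = 12 and CV 23%, the chance that the 90% interval lies within 80–125% is 46% at a true ratio of 1, 44% at 0.974 and 1% at 0.748. At 0.974, 80% power would need 22 subjects (84.0%). At 0.748 no sample size reaches it, because the true ratio is itself outside the range.

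**5. Which value is likelier.** Three places fit 29.8: the ratio of 0.75 and the argument built on it in 15.4, the same text in SAP 3.5, and the Rationale, which reports a lower fed Cmax and confines bioequivalence to AUC. A drop from 22.9 to 22.3 is under 3% and would hardly merit that contrast. Section 15.4 also says that the earlier Cmax ratio missed the bioequivalence range. The earlier study's size is not given; assuming 12 to 36 subjects at CV 23%, a ratio of 0.974 would have had a 90% interval of 0.82–1.15 to 0.89–1.07, wholly inside the range. Only Table 3 fits 22.9.

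**The case for a change.** The strongest case for action is that the documents alone cannot prove which cell is wrong, and that the protocol itself uses 80–125% both to interpret the earlier food effect and to set Cmax aside. If Table 3 were right, the sentence excluding Cmax from the sizing would be false. The trial would have only 44% power to show the absence of a Cmax food effect, and neither document gives an expected precision for a primary measure. A reader of the background alone would also be misled about the main prior evidence on this trial's own question.

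Part of this stands. The inconsistency is genuine, the ACH-CYT-01 report is the place to settle it, and a stated interval factor of about 1.18 would be informative. The rest is weaker. No success criterion is set for Cmax, so the 44% and the 22 subjects measure a conclusion that the plan does not promise. The 1% figure is not a defect, since an interval should not fall within 80–125% when food truly lowers Cmax by a quarter. Nor, under the likelier value, would the result be ambiguous: the expected interval lies wholly below 1.

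**Conclusion.** The concern identifies a real discrepancy, most likely a clerical slip in Table 3, and it does not call for a change to the plan. Replacing one fasted value with the other leaves the calculated 4 subjects, the planned 12, the log-scale ANOVA, the 90% interval and its expected factor of 1.18 all as they are. The plan already confines its claim of sufficiency to AUC and disclaims a formal bioequivalence comparison, so a precision statement for Cmax would add detail without altering what is done or concluded.

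This rests on the stated CV of 23% holding for the new formulation in smokers, on all 12 subjects contributing both periods, and on 29.8 being the correct value, which the internal evidence favours but does not prove. If the ACH-CYT-01 report showed 22.9 to be correct, the sentence giving the reason for setting Cmax aside in protocol 15.4 and SAP 3.5 would be wrong, along with the 29.8 and 0.75 it relies on. The AUC-based sample size and the planned analyses would still be unaffected.
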